An attended, in-laboratory, nighttime PSG remains the gold standard for diagnosis of OSA; however, it does not provide information on the site of obstruction, or direct further therapies. The pathophysiology underlying upper airway collapse in hypotonic conditions is frequently multi-factorial and multi-site, with diffuse, poor muscle tone control. As such, traditional treatment modalities are frequently ineffective. The initial step in treatment of pediatric OSA in children with or without HUAO is considered to be adenotonsillectomy. Whereas adenotonsillectomy is curative in 36%-80% of otherwise healthy children with OSA [10], patients with hypotonia often have persistent severe OSA post-adenotonsillectomy, with minimal improvement in the severity of sleep apnea [3]. PAP delivered via nasal or full-face mask is a widely accepted therapy for persistent OSA particularly in older children, with only 50% or fewer adherent to therapy. However, children with HUAO, with manifestations of developmental delay and intellectual impairment, have significant challenges with PAP adherence [11,12]. In addition to poor adherence, PAP has significant drawbacks. Aerophagia, risk of aspiration either secondary to gastroesophageal reflux, or primary aspiration of oral secretions, may prompt concern for exacerbation of these comorbid conditions commonly seen in HUAO. Furthermore, risk of aspiration in conjunction with a patient's inability to remove a PAP mask themselves poses a catastrophic potential.

Therefore, children with HUAO frequently require aggressive surgical treatments to relieve the obstruction. Tracheostomy, by bypassing upper airway obstruction, definitively treats upper airway obstruction, but at the cost of a highly invasive surgical intervention. Tracheostomy

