### 9.4 R33 Phase – Randomization

After the R61 phase is successfully completed, for the R33 phase we will recruit 40 children with HUAO meeting the inclusion criteria of severe OSA (AHI>10 or >5 with hypoxemia) with the additional requirement that all subjects require the presence of at least one symptom of OSA (such as snoring 3 or more nights per week, daytime sleepiness, or hyperactive/inattentive behaviors). These latter symptoms will identify children at the highest risk for OSA and will minimize false positive from the baseline PSG. The exclusion criteria are the same as those delineated in the R61 phase clinical study.

Recruitment will occur from all clinics as well as community sources. In order to ensure that sufficient children complete the protocol and we have enough data from 40 subjects for our data analysis, we may recruit up to a total of 50 subjects to include for those children who may drop out before the end of 8 weeks study. All children will undergo a baseline PSG to determine eligibility and establish baseline data. All families will complete a questionnaire battery at the time of baseline PSG to acquire baseline measures. Eligible patients will be randomized 1:1 to receive (1) immediate therapy with the ssNPA device or (2) standard of care (SoC). The study will be designed as a randomized wait-list controlled clinical trial such that all children stand to benefit. Randomization will be stratified by baseline AHI scores (AHI>30 vs.  $\leq 30$ ).

At 8 weeks the ssNPA group will be able to continue the ssNPA for an additional 8 weeks while the SoC group will be offered the ssNPA for 8 weeks. At the end of the 8 week period, all children will undergo an in-laboratory PSG and repeat the questionnaire battery.

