#### *10.1.1 Statistical power calculation for sample size (R33 phase):*

While we have demonstrated resolution of extremely severe OSA in our initial patients with hypotonia, the sample size calculation for the current trial is based on conservative assumptions. We defined a treatment response as meeting both a 50% reduction in AHI (e.g., 12.8 to 6.4) and post-treatment AHI<15 at Week 8. We considered this as the clinically meaningful improvement and designed the study to detect a difference in the proportion of children meeting clinically

meaningful improvement in OSA of 60% in the ssNPA device group vs. 18% in the SoC group. To detect a between-group difference of 60% vs. 18%, we will enroll 20 children per arm, for a total of 40 children, which will provide 80% power using a two-sided 0.05 level test. The study power will differ by the various assumptions. In particular, if the treatment response occurs in 15% or 20% of the ScC group enrollees, the proposed sample size will provide 75% and 86% power to detect the respective between-group differences in treatment response. We note that if a patient requires a tracheostomy within the 8 weeks of randomization, the patient will be considered not to have a treatment response. We expect further adjusting the primary analysis for baseline values of AHI will likely increase the power to detect the meaningful difference. For continuous outcomes such as PSQ or PedsQL, the proposed sample size is expected to give 80% power to detect an effect size of 0.89 SD or larger. We conservatively assume up to 20% dropout from the study where neither a tracheostomy nor a PSG is done, and to ensure that a total of 40 children have complete outcome data, we will enroll 50 children.

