### *10.2.2 R33 Phase Statistical analysis:*

We will summarize subject characteristics by study arm. We will also summarize outcomes data at each assessment time and changes from baseline in outcome measures at each follow-up time by arm using appropriate summary measures including means, standard deviations, and proportions. If the data are highly skewed such as increasing variability with increasing mean, we will consider log-transformation. Primary outcomes will be treatment response at Week 8, defined as a clinically meaningful improvement in AHI of 50% reduction and AHI<15, and primary analytic cohort will be intent-to-treat. For the comparison of treatment response, receiving tracheostomy prior to Week 8 will be considered a treatment response failure. Although post treatment data are collected at Weeks 8 and 16, primary comparative analysis will be done using Week 8 data as the SoC group patients initiating the ssNPA at Week 8 will have self-selected to use the device and are not parallel to those initially randomized to the ssNPA. The between-arm difference in treatment response will be compared using a two-sample proportion test. Secondary outcomes will include various patient and caregiver outcome measures including AHI, PSQ, PedsQL and OSA-18. Improvement in each of these continuous measures will be compared between arms using mixed models with data at both baseline and Week 8 as the dependent variables, participants as random intercepts and an indicator for the ssNPA arm, an indicator for Week 8, and an interaction of Week 8 by ssNPA arm as the primary predictors. The parameter of the Week 8 by ssNPA arm interaction term will estimate the ssNPA effect. We will separately

report dropouts by arm and collect data on reasons for dropping out of the study. If dropout rate is more than 10%, for each outcome variable, we will perform an alternate parallel analysis where we will weigh the between-arm response comparisons inversely by the propensity of dropping out, with the propensities estimated separately from a logistic regression predicting dropout using baseline patient characteristics (e.g., age, sex, baseline AHI, treatment arm).

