In secondary analyses, we will use linear mixed models and fit longitudinally assessed outcomes data at baseline, Weeks 8 and 16 to assess the long-term effects of ssNPA. For binary treatment response, the outcomes assessed at Week 8 and 16 will be modeled using a generalized mixed model with logit link. The model will include participants as random intercepts and will include the ssNPA arm indicator, categorical time indicators for Weeks 8 and 16, and interactions of Week 8 by arm and Week 16 by arm. A significant interaction of Week 8 by ssNPA arm will provide evidence for ssNPA effect, and showing no difference in the coefficients between the two interaction terms of Week 8 by ssNPA arm and Week 16 by ssNPA arm will indicate NPA effect to remain long-term over the 4-month period. Prior to the longitudinal data modeling, we will graph cross-sectional means of outcome measures (e.g., percentage with treatment response) with SoC group stratified further to those that opted to receive ssNPA at Week 8 vs. not to visualize if their Weeks 8 and 16 data should be treated as a separate group or can be treated as additional data to ssNPA arm data. The data and model will allow us to explore for sub-hypotheses if the number of SoC group patients receiving ssNPA at Week 8 is substantial. We note, however, that the Week 16 outcomes of SoC group patients will be interpreted carefully as they reflect outcomes in participants who opt to use or not use ssNPA after having been exposed to the standard care under a research setting for an 8-week period.

Of critical importance will be subgroup of patients who have OSA severity with AHI>30. These Patients with HUAO and extremely severe OSA are likely to fail surgical interventions other than tracheostomy and as such will be considered “warranting tracheostomy”. Given the proposed sample size and the known prevalence of about 20% of hypotonic patients with severe apnea, we expect a total of about 8-10 patients “warranting tracheostomy”. We will report, by each arm, the number (%) receiving tracheostomy in all study enrollees and in those with baseline AHI>30 by Week 8. We will also report the number (%) receiving tracheostomy in those randomized to ssNPA arm by Week 16. These data will be used for future power calculations to determine sample size requirements for larger trials focused on the utility of the ssNPA in tracheostomy avoidance.

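### The rule that a tracheostomy counts as non-response stops at Week 8, so a child with a tracheostomy can count as a Week 16 responder and support a lasting device effect

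*Combined protocol and SAP*

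**What the plan says.** The rule appears twice in the combined protocol and SAP. Section 10.1.1 (power calculation) says that "if a patient requires a tracheostomy within the 8 weeks of randomization, the patient will be considered not to have a treatment response". Section 10.2.2 (R33 analysis) says: "For the comparison of treatment response, receiving tracheostomy prior to Week 8 will be considered a treatment response failure". Both statements concern binary treatment response and the period up to Week 8. They differ in trigger: the first acts when a tracheostomy is needed, the second when one has been done.

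The secondary analyses in section 10.2.2 go further. "For binary treatment response, the outcomes assessed at Week 8 and 16 will be modeled using a generalized mixed model with logit link". Continuous outcomes, AHI among them, are compared at Week 8 and then modelled over baseline, Week 8 and Week 16. The plan takes similar arm-by-time interactions at Weeks 8 and 16 as evidence that the device effect persists over four months. None of this text mentions tracheostomy.

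The only other handling is descriptive. Tracheostomies are counted by arm up to Week 8, overall and for baseline AHI above 30. After that, "We will also report the number (%) receiving tracheostomy in those randomized to ssNPA arm by Week 16".

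Three further passages bear on the point. Section 1.1 says that tracheostomy "definitively treats upper airway obstruction, but at the cost of a highly invasive surgical intervention". Sections 9.4.1 and 9.4.2 schedule a Week 16 PSG in both arms and exempt nobody who has had a tracheostomy. Section 9.4.2 allows tracheostomy during the trial, but expects most families to choose palliative care instead.

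**The concern.** A child tracheostomised between Weeks 8 and 16 falls under no failure rule. For a child tracheostomised before Week 8, the plan does not say that the failure carries to Week 16. If the operation relieves the obstruction, as section 1.1 says it does, the Week 16 PSG would be expected to show a low AHI, and the child would meet the response definition.

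In the ssNPA arm, a child for whom the device was not enough would then raise Week 16 response and support the conclusion of a lasting effect. In the SoC arm, surgery would raise Week 16 response and narrow the contrast between arms. Continuous AHI has the same gap at both visits, because no tracheostomy rule is attached to it. The plan itself foresees tracheostomies up to Week 16, since it intends to count them in the ssNPA arm.

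**Working it through.** **Step 1. The plan's own figure, to see whether the primary analysis is touched.** Inputs, from sections 10.1.1 and 9.4: "To detect a between-group difference of 60% vs. 18%, we will enroll 20 children per arm", "which will provide 80% power using a two-sided 0.05 level test", and "Eligible patients will be randomized 1:1 to receive" device or SoC. Pooled two-proportion test:

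- mean proportion = (0.60 + 0.18)/2 = 0.39
- SE under no difference = √(2 × 0.39 × 0.61/20) = 0.1542
- SE under the alternative = √((0.60 × 0.40 + 0.18 × 0.82)/20) = 0.1392
- z = (0.42 − 1.96 × 0.1542)/0.1392 = 0.845, so power = 80.1%

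The stated 80% reproduces. The failure rule already covers this endpoint, so nothing below changes it.

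**Step 2. What the rule covers.**

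| Analysis | Visit | Tracheostomy before Week 8 | Tracheostomy in Weeks 8-16 |
|---|---|---|---|
| Binary response, primary | Week 8 | failure | does not arise |
| Binary response, logit mixed model | Week 16 | not stated | no rule |
| Continuous AHI | Week 8 | no rule | does not arise |
| Continuous AHI, longitudinal | Week 16 | no rule | no rule |
| Tracheostomy count | by Week 16 | ssNPA arm only | ssNPA arm only |

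**Step 3. Would such a child meet the response definition?** Response needs a 50% reduction and AHI below 15. For a baseline above 30, half the baseline exceeds 15, so AHI below 15 is the binding condition. At baselines of 40, 60 and 114, half the baseline is 20, 30 and 57. Any post-tracheostomy AHI below 15 therefore makes the child a responder. The documents give no post-tracheostomy AHI. That it would be below 15 is an inference from section 1.1.

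**Step 4. Size for Week 16 response.** The documents give no tracheostomy rate, so 1-2 children in an arm of 20 is assumed.

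- one child: 1/20 = 5 points
- two children: 2/20 = 10 points

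Illustration: at the planned 60%, 12 of 20 ssNPA children respond at Week 8. Suppose those 12 still respond at Week 16 and two of the other eight have a tracheostomy in between. Week 16 response is 14/20 = 70% as the plan is written, and 12/20 = 60% if tracheostomy counts as non-response.

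**Step 5. Size for continuous AHI.** With complete data at baseline and Week 8, the Week 8 by arm interaction equals the difference in mean change. Compared with no change from baseline, one tracheostomised child moves the arm's mean change by (baseline AHI − AHI afterwards)/20. Assumed AHI afterwards is 2. Assumed baselines are 40, 60 and 114; the last is the highest pilot value, in section 11.3.1.

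- baseline 40: 38/20 = 1.9 events/h
- baseline 60: 58/20 = 2.9 events/h
- baseline 114: 112/20 = 5.6 events/h

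Two such children double these to 3.8, 5.8 and 11.2 events/h.

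**The case against.** The strongest reply is that only secondary analyses are involved and that the event should be rare. Both parts stand. The Week 8 endpoint is protected, and section 9.4.2 expects low uptake. A reader might take the 8-10 children described as warranting tracheostomy in section 10.2.2 as an expected number of operations. That phrase labels children with baseline AHI above 30 and predicts no procedures.

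A second reply is that failure before Week 8 naturally carries forward. That reading is possible, though the text does not say it, and it cannot reach a tracheostomy in Weeks 8-16. For the same reason, a reader should not infer that every such child is a failure in the primary analysis and a success later. That clash can arise only for a tracheostomy before Week 8 followed by a Week 16 PSG.

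A third reply is that AHI after tracheostomy in the SoC arm is a real outcome of standard care, which may include tracheostomy. Under a treatment-policy reading this is fair. The defect is that no strategy is named; observed values are not wrong in themselves. It does not help the ssNPA arm, where the question is whether the device effect lasts. The plan's caution about Week 16 SoC data concerns self-selected device uptake and does not address tracheostomy.

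Two further inferences go too far. One is that the dropout weighting misses a tracheostomised child who has no PSG. Section 10.1.1 leaves such a child out of its dropout allowance, but section 10.2.2 does not define dropout for the weighting, so this is only unclear. The other is that a Week 16 SoC count would supply a randomised comparator. SoC children are offered the device at Week 8, so it would not.

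**Conclusion.** The gap is real and confined to the secondary analyses. Week 16 binary response has no rule for a tracheostomy in Weeks 8-16 and no stated carry-forward of an earlier one, yet it supports the plan's conclusion about a lasting effect. If 1-2 children in an arm of 20 are affected, that arm's Week 16 response moves by 5-10 points. The bias favours the device when they are in the ssNPA arm and works against it when they are in SoC. Continuous AHI has no rule at either visit. One child moves an arm's mean change by about 2-6 events/h relative to no change.

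These sizes rest on an assumed number of tracheostomies and, for continuous AHI, an assumed AHI of 2 afterwards. The omission itself is certain; whether it will matter in practice is not. A reader might infer that the primary result or its power is compromised, but Step 1 shows that it is not.

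**What to change.** - **Binary response.** State that a child who receives a tracheostomy before a scheduled PSG is a non-responder at that visit and at all later visits, including Week 16. Use one trigger in sections 10.1.1 and 10.2.2, so that needing and receiving a tracheostomy are not treated as the same event by accident.
- **Continuous AHI.** Report the mixed models with and without post-tracheostomy values as a sensitivity analysis, and say in advance which is the main one. Substituting the baseline value is one option and not a requirement. It treats an imputed value as observed, and it can favour the device when the tracheostomy is in SoC.
- **Counts.** Report tracheostomies by Week 16 in both arms, with SoC split by ssNPA uptake, as description only.

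The cost is a few sentences in the analysis section, one extra analysis and one extra table row. No new data are needed. The downside is that Week 16 response may look slightly less favourable. The changes should be made before any unblinded analysis.

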Prior to study enrollment, tours of the sleep laboratory will give subjects and families a preview of that environment and equipment used there, reduce any possible fears or anxieties, and give them a good understanding of study requirements in relation to family, school, and job commitments. Technicians experienced with children, including children with developmental disabilities, and anxieties of this age group will conduct sleep studies. One parent will stay with each child during overnight testing to reduce separation anxiety. Spacious pediatric sleep rooms are designed to include a separate bed for the parent. During sleep studies, a physician investigator will always be on call for any unexpected emergencies. Studies will be performed in the 12-bed Michael S. Aldrich Sleep Disorders Laboratory, Division of Sleep Medicine, where a 24-hour technical staff including pediatric and research technologist pods is well prepared to meet the needs of children and families who participate in research. Finally, every effort will be made to ensure, as in the investigators' past NIH-funded pediatric sleep protocols, that this research experience is fun, positive, and rewarding for each subject and family.

Problems with ssNPA use will be preempted in part by thorough education of parents, and children, about the purpose, potential benefits, and importance of nightly adherence. Participating families will be well educated about potential problems, and what to do about them, even before starting ssNPA therapy. The device has demonstrated initial safety and efficacy in a pilot group of 4 patients with severe OSA (apnea/hypopnea index, or AHI, as high as 114/hour). The NPA devices will have a series of sizes (lengths and silicone attachment sizes) available for otolaryngologist to choose. The otolaryngologist will then determine the optimal size for each child to achieve the best fitting and appropriately bypass the obstruction. This will minimize risk for discomfort or irritation. After ssNPA therapy is initiated, contact initially with study team members will occur daily during the first week of using the device and will continue during following weeks if needed and will provide multiple opportunities to detect and correct problems. Use of ssNPA on every night will be encouraged: parents and children will be educated about its importance.

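### Section 10.1.1 expects power to rise from adjusting the primary analysis for baseline AHI, but Section 10.2.2 specifies only an unadjusted test

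*Combined protocol and SAP*

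**What the plan says.** Section 10.2.2 gives one method for the primary outcome: "The between-arm difference in treatment response will be compared using a two-sample proportion test". It mentions no covariate or stratum.

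Section 10.1.1 sizes the trial at 20 per arm for 60% versus 18% response, "which will provide 80% power using a two-sided 0.05 level test", and then adds: "We expect further adjusting the primary analysis for baseline values of AHI will likely increase the power to detect the meaningful difference". It names no model.

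Section 9.4 says "Randomization will be stratified by baseline AHI scores", with a cut at 30. It does not say how the stratum is to be used in the analysis.

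Baseline AHI does enter the response endpoint itself, which requires a halving of AHI and a Week 8 value below 15. Otherwise, for response, it appears only in the model for dropout weights, a "logistic regression predicting dropout using baseline patient characteristics (e.g., age, sex, baseline AHI, treatment arm"), used if dropout exceeds 10%. The longitudinal logit model for response "will include the ssNPA arm indicator, categorical time indicators for Weeks 8 and 16", plus their interactions and a random intercept. It has no baseline AHI term.

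For AHI, PSQ, PedsQL and OSA-18, Section 10.2.2 fits baseline and Week 8 values jointly, with terms for arm, Week 8 and their interaction. The interaction is the treatment effect.

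**The concern.** The power section describes a feature of the primary analysis that the analysis section does not contain. Its form is also open: Section 10.1.1 speaks of AHI values, which suggests a continuous covariate, whereas Section 9.4 uses two classes. A stratified test, a logistic model and a model giving a standardised risk difference would all fit the sentence in Section 10.1.1.

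With 40 children, an adjusted and an unadjusted test can fall on different sides of 0.05. If the role of the adjusted analysis is not fixed in advance, that choice could be made after the results are seen. It is also worth checking whether the expected gain in power is as likely as the plan suggests.

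**Working it through.** **1. The plan's own figure.** Inputs from Section 10.1.1: p1 = 0.60, p2 = 0.18, n = 20 per arm, two-sided 0.05. The pooled rate is (0.60 + 0.18)/2 = 0.39.

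- Standard error under the null: sqrt(0.39 × 0.61 × 2/20) = 0.1542
- Standard error under the alternative: sqrt((0.60 × 0.40 + 0.18 × 0.82)/20) = 0.1392
- Power: Φ((0.42 − 1.96 × 0.1542)/0.1392) = Φ(0.845) = 80.1%

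Full enumeration of the same uncorrected test gives 80.5%. The stated 80% is therefore that of the unadjusted test and includes no gain from adjustment.

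**2. Is baseline AHI prognostic for response?** The documents give no response rates by stratum. The endpoint requires a fall of max(50%, 1 − 15/AHI): 50% at AHI 30, 1 − 15/40 = 62.5% at AHI 40, and 1 − 15/60 = 75% at AHI 60. Response is therefore harder to reach above 30. Against that, Section 11.3.1 says "The device has demonstrated initial safety and efficacy in a pilot group of 4 patients with severe OSA", with AHI up to 114 per hour. The direction is open, so the check has to run over assumed rates.

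**3. What a stratified test would do.** Section 10.2.2 puts the share above AHI 30 at about 20% ("Given the proposed sample size and the known prevalence of about 20% of hypotonic patients with severe apnea"), so 0.20 × 20 = 4 per arm above and 16 at or below. For an assumed rate h above 30, the rate at or below 30 is (overall − 0.2h)/0.8, which keeps the overall rates at 60% and 18%. All outcomes were enumerated for the pooled two-sample test and for the CMH test without continuity correction.

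| Assumed response above AHI 30 (ssNPA / SoC) | Unadjusted power | CMH power |
|---|---|---|
| 60% / 18% (not prognostic) | 80.5% | 78.9% |
| 80% / 10% | 80.8% | 78.8% |
| 60% / 5% | 80.7% | 79.4% |
| 50% / 10% | 80.6% | 79.8% |
| 30% / 5% | 81.2% | 83.2% |
| 10% / 5% | 82.1% | 86.4% |
| 10% / 0% | 82.3% | 87.2% |

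The change runs from about −2 to +5 points, and three of the six prognostic cases lose power. Over a wider grid of 225 assumed pairs the worst loss is 2.7 points, and CMH gains in 51%. In the seven cases shown, the two tests disagree on significance in 2.3% to 5.1% of trials.

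**4. Level.** Over 373 null settings (common rate 15% to 60%, rate above AHI 30 no higher), CMH has a level of 4.2% to 5.4% and the unadjusted test 1.0% to 5.3%. For example, at a common 39% with 10% above AHI 30, CMH is at 5.3% and the unadjusted test at 3.9%.

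**5. Continuous secondary outcomes.** With complete data, the interaction equals the between-arm difference in mean change. With equal variance σ² at both visits and baseline to Week 8 correlation r, the variance per child is 2(1 − r)σ² for change and (1 − r²)σ² with baseline adjustment. The ratio is (1 − r²)/(2(1 − r)) = (1 + r)/2, which is 0.65, 0.75 and 0.85 at assumed r = 0.3, 0.5 and 0.7. Simulation with 20 per arm gave 0.67, 0.77 and 0.88. The gain disappears near r = 0.95.

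**The case against.** The strongest reply is that there is no direct contradiction. The sentence in Section 10.1.1 is a hedged expectation and can be read as describing a supplementary analysis. The analysis section names one test, and that test matches the power calculation. This largely stands: a reader following Section 10.2.2 knows what will be run. What remains is that the sentence refers to the primary analysis, and no adjusted analysis is given a form or a role anywhere.

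A second reply is that the CMH figures test a dichotomised adjustment, whereas Section 10.1.1 refers to AHI values. That also stands. A small simulation with a logistic likelihood-ratio test and an assumed log-AHI distribution (3,000 trials per case) gave 80.6% unadjusted versus 81.6% adjusted with no AHI effect, and 80.5% versus 87.4% at a log-odds of −1 per SD. The level of that test was not checked at this sample size, so these figures do not settle the matter. They do show that the losses in the table should not be carried over to continuous AHI.

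A reader might infer that the trial is underpowered without the adjustment. The documents do not support this, because the 80% is already the unadjusted figure. A reader might also infer that stratified randomisation makes an unadjusted test invalid. Section 9.4 makes no such demand, and in the null settings above the unadjusted level stayed between 1.0% and 5.3%, mostly a matter of lost efficiency rather than false positives.

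**Conclusion.** The point holds as a gap between two sections: an adjustment is anticipated for power, but baseline AHI is not a covariate or stratum in any response comparison. The practical effect is modest. Sample size and validity are not affected, with one qualification: the 80% holds for the uncorrected two-sample test, and Section 10.2.2 does not say which version is meant (Fisher's exact test would give 71.2%).

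For the CMH option only, with 4 + 16 children per arm and assumed stratum rates, power moves by about −2 to +5 points and the level can reach 5.4%. A gain is therefore possible but not assured. Nothing in the documents fixes the stratum rates, so no single value within that range can be preferred.

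The secondary-outcome model is valid. The point there is precision alone, and it rests on equal variances at the two visits and on an r that the documents do not give.

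**What to change.** In Section 10.2.2, commit to one primary analysis that uses baseline AHI. The simplest is a CMH test by the randomisation stratum (AHI above 30 versus 30 or below), reported with the Mantel-Haenszel risk difference and 95% CI. If the team wants what Section 10.1.1 describes more literally, name a model with continuous baseline AHI and a standardised risk difference instead, and check its power and level first. Either way, keep the unadjusted test as a sensitivity analysis and reword Section 10.1.1 to match.

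If the unadjusted test is to stay primary, say so, label the adjusted analysis supportive, and delete the power expectation from Section 10.1.1.

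Minor addition: for AHI, PSQ, PedsQL and OSA-18, drop the arm main effect so that the arms share a baseline mean, or use ANCOVA on baseline.

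All of this is wording; the stratum and baseline values are already collected. The cost of the CMH route is a possible power loss of about 2 points (2.7 at worst on the wider grid) and a level that may slightly exceed 5%. Keeping the unadjusted test as primary has no statistical cost, but gives up any gain from adjustment.

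### The dropout-weighted analysis divides by the probability of dropping out instead of the probability of being observed, which reverses the weights

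*Combined protocol and SAP*

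**What the plan says.** Section 10.2.2 makes the weighted analysis conditional on dropout: "If dropout rate is more than 10%, for each outcome variable, we will perform an alternate parallel analysis". In it, "we will weigh the between-arm response comparisons inversely by the propensity of dropping out", and the propensities come from a "logistic regression predicting dropout using baseline patient characteristics", for example age, sex, baseline AHI and arm. Both halves of the rule name dropout as the modelled event. Nowhere is the weight defined as the inverse of the probability of remaining in the study.

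Section 10.1.1 sets the expected scale: "We conservatively assume up to 20% dropout from the study where neither a tracheostomy nor a PSG is done". It enrols 50 children so that 40 have complete data. On the response endpoint, "receiving tracheostomy prior to Week 8 will be considered a treatment response failure", so such a child has a known outcome. Separately, the plan will "report dropouts by arm and collect data on reasons for dropping out of the study".

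**The concern.** Only children with an observed Week 8 outcome can enter the response comparison. Inverse-probability weighting repairs selective loss by letting each observed child also stand in for similar children who were lost. Those who most resemble the dropouts must therefore count for more. A weight of 1/p does the opposite: it counts them for less and enlarges the imbalance left by the dropout.

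A check meant to show whether dropout distorted the result could then move the estimate further from the truth than no adjustment. This happens when dropout depends on the modelled covariates and those covariates also modify the treatment effect, or when the dropout pattern differs by arm. It is the only adjusted analysis the plan names for dropout, so a reader would rely on it for reassurance about the primary response result.

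The sentence also covers every outcome variable without saying what counts as missing for each. A child with a tracheostomy before Week 8 has a known response but may have no Week 8 AHI.

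**Working it through.** **Inputs from the documents.** Response 60% on ssNPA vs 18% on standard of care (SoC), 20 evaluable children per arm, dropout up to 20%, 50 enrolled (section 10.1.1). Share with AHI above 30: about 20%, from "the known prevalence of about 20% of hypotonic patients with severe apnea, we expect a total of about 8-10 patients" (section 10.2.2). The plan's own figures reproduce: the pooled two-proportion formula with 20 per arm gives 80.1% power, and 40/(1 − 0.20) = 50.

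**Step 1: the weights (no assumption about the data).** 1/p falls as p rises; 1/(1−p) rises.
- p = 0.15: 1/0.15 = 6.67 as stated; 1/0.85 = 1.18 correct.
- p = 0.40: 1/0.40 = 2.50 as stated; 1/0.60 = 1.67 correct.

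Relative to the low-dropout child, the high-dropout child counts 2.50/6.67 = 0.375 as stated, against 1.67/1.18 = 1.42 when correct.

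**Step 2: effect on the response difference.** The documents give no rates by AHI stratum, so these are assumed: response for AHI ≤30 / >30 of 67.5% / 30% on ssNPA and 20% / 10% on SoC. They average to the plan's figures: 0.8 × 67.5 + 0.2 × 30 = 60 and 0.8 × 20 + 0.2 × 10 = 18. The true difference is 42.0 points.

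For a stratum with share f, dropout d and weight w, the weighted contribution is f(1−d)w. Let s be the AHI>30 contribution divided by the total. When both arms have the same dropout pattern, the difference is (67.5 − 20)(1 − s) + (30 − 10)s = 47.5 − 27.5s.

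Worked case, dropout 15% / 40%. The completer shares are 0.8 × 0.85 = 0.68 and 0.2 × 0.60 = 0.12.
- Unweighted: s = 0.12/0.80 = 15.0%; difference 43.4.
- As stated: 0.68/0.15 = 4.533 and 0.12/0.40 = 0.300; s = 0.300/4.833 = 6.2%; difference 45.8.
- Correct: 0.68/0.85 = 0.80 and 0.12/0.60 = 0.20; s = 20%; difference 42.0.

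Each pattern below has 20% dropout overall:

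| Dropout, AHI ≤30 / >30 | s unweighted | s as stated | Difference unweighted | Difference as stated | Difference with 1/(1−p) |
|---|---|---|---|---|---|
| 15% / 40% | 15.0% | 6.2% | 43.4 | 45.8 | 42.0 |
| 17.5% / 30% | 17.5% | 11.0% | 42.7 | 44.5 | 42.0 |
| 10% / 60% (extreme) | 10.0% | 1.8% | 44.8 | 47.0 | 42.0 |
| 22.5% / 10% | 22.5% | 39.5% | 41.3 | 36.6 | 42.0 |
| 20% / 20% | 20.0% | 20.0% | 42.0 | 42.0 | 42.0 |

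With 15% / 40% on ssNPA but 20% / 20% on SoC, the differences are 43.9 unweighted and 47.2 as stated. If the effect is instead equal in both strata (62% / 52% vs 20% / 10%), they are 42.5 and 43.4. There is no bias when dropout differs only by arm (10% vs 30%), or when the effect is equal across strata and the dropout pattern is the same in both arms.

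**Step 3: fitted propensities at the trial's size.** The simulation used 20,000 trials of 50 children (25 per arm, 5 of them with AHI above 30) and a logistic dropout model on AHI stratum and arm. Trials were kept if 6 or more children dropped out and the model converged. At 15% / 40% (18,996 kept):

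| | Unweighted | 1/(1−p) | As stated |
|---|---|---|---|
| Mean difference, points | 43.7 | 42.2 | 45.5 |
| SD, points | 13.6 | 13.8 | 14.2 |

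Within a single trial, the result as stated differs from the correctly weighted one by 5.1 points on average, by more than 5 in 41% of trials and by more than 10 in 13.5%. Leaving the data unweighted differs by 2.2 on average and by more than 5 in 12%. With dropout unrelated to AHI (20% / 20%), the gap as stated still exceeds 5 points in 24% of trials, against 1% unweighted.

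**Step 4: chance of use.** More than 10% of 50 means 6 or more. With X ~ Binomial(50, rate), P(X ≥ 6) is 95% at a true rate of 20%, 78% at 15% and 38% at 10%.

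**The case against.** The strongest reply is that the sentence is shorthand for ordinary attrition weighting and that no competent analyst would implement a weight with no purpose. The authors may well have meant 1/(1−p). But the text gives no formula, names dropout twice as the modelled event and contains nothing that corrects the literal reading. An analyst who follows it would invert the fitted dropout probability. Settling the matter after the data are seen would turn a prespecified check into a post hoc choice.

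Other points stand as limits on the size of the problem:
- The analysis is conditional and secondary.
- The 20% dropout figure is a ceiling, so the 95% trigger probability is the upper end.
- The stratum rates are assumed, and the direction of the bias changes with them.
- The extra bias is small against sampling error. Combining bias and SD from the simulation, the root mean squared error is √(3.5² + 14.2²) = 14.6 points as stated, against √(0.2² + 13.8²) = 13.8 with correct weights and √(1.7² + 13.6²) = 13.7 unweighted.
- Part of the single-trial gap is noise, as the 20% / 20% case shows.
- For continuous outcomes the plan fits "mixed models with data at both baseline and Week 8 as the dependent variables". Children who leave still contribute baseline rows there, which gives some protection without weights. Reliance on the weighting therefore falls mainly on the binary response.

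**Conclusion.** The concern holds. The stated weight is the inverse of the wrong probability, and the reversal of the weights is certain from the wording and algebra alone. Its numerical effect is not certain. Under the assumed strata, the stated weights give differences from 36.6 to 47.2 points against a truth of 42.0. Wherever dropout bias arises in these cases, the stated weights are further from the truth than unweighted completers.

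The figures apply to the response comparison only; the plan does not say how rows in the mixed models would be weighted. The primary two-sample test, the main mixed models, the power, the reporting of dropouts by arm and the descriptive tracheostomy counts are unaffected. This should be fixed before analysis, but it does not threaten the trial's main result.

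**What to change.** Replace the weighting clause in section 10.2.2 with: for each outcome, children with that Week 8 outcome observed will be weighted by the inverse of the estimated probability that it is observed, 1/(1 − estimated probability that it is missing); for treatment response, tracheostomy before Week 8 counts as an observed failure.

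The last clause repeats the plan's existing rule for response, so that the missingness model codes those children consistently. The cost is one sentence of SAP text, with no new patients, data or analyses.
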